Slow breathwork has received most research attention so far; in our recent meta-analysis ([name] et al., 2023) we found significant small-medium effects, showing breathwork was associated with lower subjective stress (primary outcome), anxiety and depression (secondary outcomes) compared to non-breathwork controls. For the primary outcome, 10 and only 2 studies respectively comprised slow and fast breathwork; these were of moderate and high risk of bias, suggesting more robust tests of their potential effects are needed. Nonetheless, fast breathwork may offer potential therapeutic benefit as temporary voluntarily induced stress has been suggested as, and could possibly be, beneficial for health (Petraskova Touskova et al., 2022). High-intensity physical exercise can improve health by inducing a sympathetic response (stress) initially, subsequently followed by adaptation. Similarly, HVBR may induce short-term stress that can improve mental health and provisional evidence has shown it may confer beneficial therapeutic effects regarding perceived stress (Kopplin & Rosenthal, 2022). While increasing stress seemingly mitigates the improved health claims of HVBR, it might be elucidated more clearly through the notion of hormesis, an adaptive response to states of moderate bodily stress (Mattson, 2008). The key, perhaps, is that it is not done reflexively (i.e., responsive hyperventilation during a panic attack), but is performed deliberately in a controlled manner (i.e., hyperventilation during an intentional breathwork practice); and only five min/day of HVBR for four weeks has also been associated with improvements on state anxiety along with positive and negative affect (Balban et al., 2023). For example, exercise is voluntarily induced and thus is a different stressor to reactive states in response to negative stressors in life. Both RCTs of Kopplin and Rosenthal (2022) and Balban et al. (2023) display positive effects of HVBR on mental health outcomes, however such findings are limited by the quality of trial design and study methods used. For example, neither included a *placebo* control, making it difficult to establish for these studies whether the interventions had specific active effects on mood beyond attention/expectation effects. Further, more research is needed to gauge the safety profile of fast breathwork. Whilst our meta-analysis did not find negative effects directly attributed to breathwork, only six studies in total (for all outcomes) out of 26 actively reported on this. Thus, we will actively do so.

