- Does HVBR lead to improved subjective sleep-related impairment in comparison to an active placebo control in a general population adult sample at: a) post-intervention, b) follow-up?
- Does HVBR lead to improved subjective positive affect in comparison to an active placebo control in a general population adult sample: a) immediately after the first session of breathwork, b) at post-intervention.
- Does HVBR lead to improved subjective negative affect in comparison to an active placebo control in a general population adult sample: a) immediately after the first session of breathwork, b) at post-intervention.

Exploratory Hypotheses

Additionally, we want to see if pre-post changes are correlated with a) adherence (amount of breathwork practice, i.e., is there a dose response?), and b) credibility and expectancy of the breathwork intervention given. We would expect both greater adherence (in the HVBR practice arm) and credibility/expectancy to be associated with greater improvements on the outcome measures listed. If there are significant differences between groups on credibility/expectancy then covariance analysis will be explored, to test whether differences between groups in credibility/expectancy are accounting for any measured differences in outcomes at post-intervention.

Methods

Participants

200 people (100 per group) will be recruited. We will also select the balanced sample filter option on Prolific so as to distribute the study evenly across gender. A moderate effect size, statistical power and significance level of 0.50, 0.80 and 0.05, respectively, requires a sample of 128 participants (64 per group). PsyDAO, a decentralised organisation funding research at the intersection of psychedelics and mental health, provided funding for participant payments for a sample size of 200 participants, so this was the largest sample possible, and also allows for potential attrition. The two previous published RCTs of Balban et al. (2023) and Kopplin and Rosenthal (2022) had final samples of N=108 (4 groups; HVBR condition n=33) and N=86 participants (4 groups; HVBR condition n=20), respectively. The former study was adequately powered statistically, but the latter was not (actually required a sample size of 100).

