Pre-post intervention and follow-up questionnaires will be self-completed by participants online via the survey platform Qualtrics, which will be linked to Prolific. Three short scales will be used to measure trait outcomes of mental health, wellbeing and sleep-related impairment at these timepoints (baseline/pre-intervention, post-intervention, three-week follow-up): the Depression Anxiety Stress Scale (DASS-21) (Lovibond, & Lovibond, 1995), Short Warwick-Edinburgh Mental Wellbeing Scale (SWEMWBS) (Ng Fat et al., 2017), and PROMIS Item Bank v. 1.0 - Sleep-Related Impairment - Short Form 4a (PROMIS-4a) (Hanish, Lin-Dyken & Han, 2017). The primary outcome will be stress (measured using the DASS-21 stress subscale), and the primary timepoint will be post-intervention (three weeks

post-randomisation). The secondary outcomes will include: anxiety and depression (from DASS-21), mental wellbeing (SWEMWBS) and sleep-related impairment (PROMIS-4a). State measures of positive and negative affect using the Positive and Negative Affect Schedule (PANAS-20) (Watson, Clark & Tellegen, 1988) (secondary outcomes) will also be completed during the baseline survey. Immediately after starting the breathwork (first session of breathwork), participants will be asked about the credibility and expectancy of the intervention randomly allocated to them to assess if the intervention and placebo are seen as equally credible and thus merit equal expectation of benefit. This will be measured using the Credibility/Expectancy Questionnaire (CEQ-6), which is another secondary outcome. The PANAS-20 will also be completed once at this timepoint, to gauge a sense of state change due to the breathwork, in addition to once more at post-intervention. The last secondary outcomes, which will be measured post-intervention, are: negative side effects (to judge the safety and tolerability profile of the breathwork) and adherence to protocol (number of times participants self-reported practicing breathwork out of the 21 days assigned). Other outcomes include general sentiment towards the protocol (i.e., positive, negative, neutral) and open-ended questions on participants overall experiences of the protocol and/or study period. Pre-intervention, simple demographics (Age, Gender and Ethnicity) will be collected and, at follow-up, participants will be asked if they can guess which condition they were allocated to (to tentatively see if blinding was successful—see Procedure section).

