Primary outcome measure

1. Subjective stress (DASS-21 stress subscale)

Secondary outcome measures:

2. Subjective anxiety (DASS-21 anxiety subscale)
3. Subjective depressive symptoms (DASS-21 depression subscale)
4. Subjective mental wellbeing (SWEMWBS)
5. Subjective sleep-related impairment (PROMIS-4a)

[All of above outcomes measured pre-post-follow-up]

6. Subjective positive affect (PANAS-20 positive affect subscale). Measured pre-intervention, after first breathwork session, and post-intervention.
7. Subjective negative affect (PANAS-20 negative affect subscale). Measured pre-intervention, after first breathwork session, and post-intervention.
8. Self-reported credibility and expectancy of protocol (CEQ-6). Measured after completing first session of breathwork.
9. Negative side effects due to protocol (whether participants experienced unpleasant/unwanted a) short-term effects, and/or b) lasting bad effects from the breathwork, to gauge safety and tolerability). Measured post-intervention.
10. Self-reported adherence to breathwork protocol (number of sessions participants self-report practicing out of 21 days assigned). Measured post-intervention.

Other—Overall experience, Hypothesis guessing, Attention checks

Optional questions on participants' perspectives and overall experience of the protocol (post-intervention) / study-period (follow-up), and if they can correctly guess which condition they were allocated to (follow-up). Lastly, The DASS-21, SWEMWBS, PROMIS-4a, and PANAS-20 will all have one attention-check question in them to ensure participants are completing the surveys properly.

Procedure

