Secondary outcomes of positive and negative affect will be calculated from respective subscales on Positive and Negative Affect Schedule (PANAS-20). Pre-intervention, after first breathwork session, and post-intervention scale score differences between groups will be analysed through mixed analysis of variance. Self-reported credibility and expectancy of the breathwork protocol will be measured via the Credibility/Expectancy Questionnaire (CEQ-6). Descriptive statistics for all measures for all participants in each condition will be reported. Missing items within scales will be replaced using the mean for other items in the scale/subscale in cases where $\leq 30\%$ of data are missing from a scale/subscale or where whole scales/subscales are missing. Multiple imputation will be used where $> 30\%$ of data are missing from a scale/subscale or where whole scales/subscales are missing. Cronbach's alphas will be used to assess internal consistency of each scale at baseline. The DASS-21, SWEMWBS, PROMIS-4a and PANAS-20 all have one attention-check question in them to ensure participants are completing the surveys properly.

Primary analysis

Intention-to-treat; post-intervention is the primary timepoint for primary outcome stress. For both the primary outcome and secondary scale outcomes, group x time effects at the $p < .05$ level will be determined using mixed ANOVAs. Group x time effects at the $p < .05$ level will be followed up with simple contrasts (with pre-intervention as the comparator) and between-group t-tests. Baseline data will be controlled for depending on the outcome being tested (i.e., DASS-21 Stress at baseline will be entered as a covariate when testing effects on DASS-21 Stress). Data analysis will be performed in R and SPSS.

Secondary analysis

Per-protocol analysis (participants reporting at least 10 sessions of the breathwork) will be conducted as secondary analysis.

Sensitivity checks

If sizeable missing data are present at the primary timepoint of post-intervention (6% or above), they will be replaced using multiple imputation using 30 imputed datasets and entering any study variable that predict missingness or outcomes into

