the imputation model, and used for sensitivity analysis. Analysis without baseline covariates will be included as sensitivity analysis. If a participant answers more than one of the attention-items incorrectly at each timepoint their data will be excluded from the main analyses but included in a sensitivity analysis.

Exploratory analysis of secondary measures

Adherence to breathwork protocol

Post-intervention, participants will answer how many times they completed the guided breathwork out of the assigned 21 days. This will be compared between groups via unpaired t-test, and correlated with outcome scale scores on DASS-21, SWEMWBS, PROMIS-4a and PANAS-20 within each condition to see whether there are any associations between adherence and changes in these scale scores. Adherence will be looked at as a moderator.

Credibility & expectancy of breathwork protocol

CEQ-6 scores will be compared between groups via unpaired t-tests. If there are significant differences between groups on credibility/expectancy, primary tests will be run again with this used in covariance analysis. Similar to adherence, CEQ-6 scores will be correlated with the outcome scale scores above, to see whether there are relationships between CEQ-6 and changes in these scale scores within each condition.

Negative side effects due to protocol

Whether participants experienced: 1) Unpleasant/unwanted short-term effects and/or 2) Lasting bad effects from the breathwork. Analysis will be content analysis.

Other outcomes (qualitative)

Below outcomes will be explored to offer complementary findings to main quantitative analyses above.

Overall Experience

Participants' perspectives and overall experience of the breathwork protocol and study-period (i.e., positive, negative, neutral, general notes, etc.) post-intervention and follow-up. At post-intervention, analysis will be sentiment analysis, based on whether a participant reported their overall experience of the breathwork as strongly positive, positive, neutral, negative, or strongly negative.

Hypothesis Guessing

Whether participants can correctly guess which condition they were allocated to, at end of follow-up questionnaire, to tentatively infer if blinding was successful.

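### The exploratory CEQ-6-adjusted rerun cannot show whether expectancy explains the outcome difference, and a non-significant CEQ-6 test cannot show that the two audios were equally credible

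*SAP*

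**What the plan says.** The SAP, under Credibility & expectancy of breathwork protocol (part of the exploratory analyses), first states: "CEQ-6 scores will be compared between groups via unpaired t-tests". It then adds: "If there are significant differences between groups on credibility/expectancy, primary tests will be run again with this used in covariance analysis". It does not say whether credibility and expectancy are tested separately, or which result triggers the rerun.

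The protocol, under Exploratory Hypotheses, has the same trigger and gives the purpose of the covariance analysis: "to test whether differences between groups in credibility/expectancy are accounting for any measured differences in outcomes at post-intervention". Under Outcome measures it gives the reason for collecting the CEQ-6: "to assess if the intervention and placebo are seen as equally credible and thus merit equal expectation of benefit".

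On timing, item 8 of the secondary outcome list reads: "Measured after completing first session of breathwork". Randomisation & blinding places allocation straight after the baseline survey. The rating therefore follows both randomisation and exposure to the allocated audio. The PANAS-20 is repeated at the same point to pick up any change in state caused by the session.

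The main model already adjusts for baseline: "DASS-21 Stress at baseline will be entered as a covariate when testing effects on DASS-21 Stress".

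Some CEQ-6 work does not depend on the trigger: descriptive statistics by condition, the t-tests themselves, and within-arm correlations with outcomes. Neither document plans a confidence interval or equivalence margin for the CEQ-6 difference, a mediation model, or a caution about adjusting for a variable measured after randomisation.

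**The concern.** The protocol criticises earlier trials because they left it unclear "whether the interventions had specific active effects on mood beyond attention/expectation effects". The CEQ-6 rerun is the plan's only between-group model aimed at the expectancy part of that question. Two steps in its logic fail.

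- **If the rerun happens.** A CEQ-6 rating given after the first session may partly reflect an early response to that session, or may share unmeasured causes with later stress. Adjusting for it can then move the group effect even if expectancy has no causal role. It can also leave the effect unmoved when expectancy does matter, if other influences pull the opposite way.
- **If the rerun does not happen.** Failing to reach significance is not evidence of equality, which is what the protocol wants to know about the two audios.

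At stake is a wrong sentence in the report: that expectancy was equal, or that it does (or does not) explain the effect.

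**Working it through.** **1. The plan's own figure.** Effect size 0.50, power 0.80 and level 0.05 (two-sided assumed) in a two-sample t-test give 64 per group, 128 in total, with power 0.801. The stated sample size reproduces.

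**2. Inputs.** From the protocol: "200 people (100 per group) will be recruited". I use 100 per arm because the CEQ-6 is taken at the first session, before most attrition. The documents give no CEQ-6 difference, correlation or level for the trigger, so differences in SD units, the correlations and a two-sided 0.05 level are assumptions.

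**3. How often the trigger misses a real imbalance, one test.** Noncentrality is d × sqrt(n/2) and the critical value t(0.975, 198) is 1.972. For d = 0.3, noncentrality is 0.3 × sqrt(50) = 2.12.

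| True CEQ-6 difference | Missed at 100 per arm |
|---|---|
| 0.2 SD | 71% |
| 0.3 SD | 44% |
| 0.4 SD | 20% |
| 0.5 SD | 6% |

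The 95% CI half-width is 1.972 × sqrt(2/100) = 0.28 SD. A result that just fails to reach significance therefore has an interval from about 0 to 0.56 SD.

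**4. Two tests, either one triggering.** If both subscales differ by 0.3 SD, independence gives 0.44 × 0.44 = 0.19. Simulation (40,000 trials per cell) gives 0.19 to 0.37 as the subscale correlation rises from 0 to 0.9. If only one subscale differs, the miss rate is about 42% (under independence, 0.44 × 0.95 = 0.42).

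**5. How far adjustment can move the effect when CEQ-6 has no causal effect.** With baseline stress B, post-intervention stress Y and CEQ-6 score C, the within-arm coefficient of C is

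bC = (r_CY − r_BY × r_CB) / (1 − r_CB²)

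and the group effect shifts by dC × bC, where dC is the CEQ-6 imbalance. Setting r_CB = r_CY = r:

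| Size of r | r_BY | Size of bC | Shift, dC = 0.5 | Shift, dC = 0.3 |
|---|---|---|---|---|
| 0.1 | 0.5 | 0.051 | 0.025 | 0.015 |
| 0.1 | 0.7 | 0.030 | 0.015 | 0.009 |
| 0.2 | 0.5 | 0.104 | 0.052 | 0.031 |
| 0.2 | 0.7 | 0.063 | 0.031 | 0.019 |
| 0.3 | 0.5 | 0.165 | 0.082 | 0.049 |
| 0.3 | 0.7 | 0.099 | 0.049 | 0.030 |
| 0.4 | 0.5 | 0.238 | 0.119 | 0.071 |
| 0.4 | 0.7 | 0.143 | 0.071 | 0.043 |

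Suppose the HVBR arm scores higher on CEQ-6 and higher scores go with lower stress, which is the association the protocol expects. A 0.50 SD stress reduction then shrinks to 0.38-0.48 at dC = 0.5, or 0.43-0.49 at dC = 0.3. With the opposite association it inflates by the same amounts. If r_CY = r_BY × r_CB, that is, CEQ-6 relates to outcome only through baseline stress, bC = 0 and there is no bias.

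For scale, the standard error of the baseline-adjusted effect at 100 per arm is sqrt(2/100) × sqrt(1 − r_BY²): 0.12 SD at r_BY = 0.5 and 0.10 SD at 0.7.

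**6. Why shrinkage does not identify expectancy.** Two constructed cases, each with a CEQ-6 imbalance of 0.35:

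- Expectancy is the whole effect, slope −0.40. The total effect is 0.35 × −0.40 = −0.14; after adjustment it is 0.
- CEQ-6 has no effect, but an unmeasured trait drives both CEQ-6 (loading 0.6) and stress (loading −0.5), and the true effect is −0.30. The slope is 0.6 × −0.5 / (0.36 + 0.64) = −0.30, so the adjusted effect is −0.30 + 0.35 × 0.30 = −0.195.

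Both shrink, and only one involves expectancy. These coefficients are chosen freely and omit baseline stress. They show the pattern, not its likely size.

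**7. Link to the planned model.** With baseline stress as covariate, the CEQ-adjusted group coefficient is the same for the post score and for the post-minus-pre change (checked by simulation, 200,000 per arm). Step 5 therefore applies to the planned contrast against pre-intervention, not to the three-timepoint omnibus test.

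**The case against.** The strongest reply is that little depends on this analysis. The plan's main protection against expectation effects is its design: a matched sham audio with retentions, the same neutral name for the technique in both arms, participant blinding and a condition-guess question at follow-up. The CEQ-6 rerun is a supplementary probe listed as exploratory. That stands. A reader might infer that the primary comparison is compromised, or that the trial cannot address expectation at all; the documents support neither.

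The two sizes also pull against each other. At 0.3 SD, where the trigger often misses, adjustment moves the effect by only 0.01-0.07 SD. At 0.5 SD, where it moves more, the trigger rarely misses. Every shift in the table is no larger than about one standard error. This also stands, and it limits the importance of the point.

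A reader might go further and say that a non-significant CEQ-6 test tells us nothing. That is too strong: at 100 per arm a 0.5 SD difference would be detected 94% of the time. Nor is it right to compute miss rates at 64 per arm as though that were expected. That is the powering number, and nothing suggests such a loss by the first session. The plural in the SAP's CEQ-6 sentence also leans towards separate subscale tests, so 44% is only one reading.

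Finally, participants must hear an audio before they can judge it, so a post-session rating suits the descriptive aim, and the planned descriptives would let a reader derive an interval. Both are fair. Neither rescues the attribution aim: the within-arm correlations use the same post-session rating, and the written decision rule is still significance.

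**Conclusion.** The point holds in a limited form and is worth considering. It is wrong as written, not merely short of detail, because the stated analysis does not deliver the stated attribution. That conclusion follows from the timing of the CEQ-6 and needs no assumed number.

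The sizes do rest on assumptions. With 100 per arm and a two-sided 0.05 level, a true 0.3 SD CEQ-6 imbalance goes undetected 44% of the time with one test, or 19-37% with two subscales that both differ and either triggering. A 0.5 SD imbalance goes undetected 6% of the time with one test, so a non-significant result does make a large imbalance unlikely. With CEQ-6 correlations of 0.1-0.4 and a baseline-outcome correlation of 0.5-0.7, bias from adjustment is about 0.02-0.12 SD at a 0.5 SD imbalance and 0.01-0.07 SD at 0.3 SD. It may be zero.

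A reader might infer that adjustment would overturn a significant result. No such rate can be given for the planned mixed ANOVA, and none is claimed. The primary test of stress is unaffected.

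**What to change.** In the SAP (Credibility & expectancy of breathwork protocol) and the protocol (Exploratory Hypotheses):

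1. Remove the significance trigger.
2. Report the between-group difference in credibility and in expectancy, each with its 95% CI, whatever the p-value.
3. Always show the CEQ-adjusted result beside the unadjusted primary result, labelled exploratory.
4. Replace the attribution aim with a statement along these lines: the CEQ-6 is measured after randomisation and first exposure, so the adjusted result is descriptive, and neither a change nor the absence of a change in the group effect will be read as showing that expectancy does or does not explain it.

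A mediation analysis with a sensitivity analysis for unmeasured confounding is optional.

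The cost is a few sentences and no new data. The downside is slightly more reporting and a more cautious conclusion about expectancy. The change does not turn the post-session rating into a clean measure of prior expectancy, and it means the adjusted model is always run, which is why the fourth item has to accompany the first.
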